1. OBJECTIVES

1.1. Primary Objective

Cohort A/B: To estimate the objective response rate (ORR) in patients with metastatic or locally advanced microsatellite stable (MSS) colorectal cancer that have a positive and negative composite PD-L1/Mucin (CPM) score treated with nivolumab and relatlimab.

Cohort C: To estimate the objective response rate (ORR) in patients with metastatic or locally advanced microsatellite stable (MSS) colorectal cancer without prospective biomarker selection treated with nivolumab and relatlimab.

1.2. Secondary Objective

1.2.1. To assess safety and characterize toxicities of nivolumab in combination with relatlimab.

1.3. Exploratory Objectives

- 1.3.1. To assess the overall survival (OS), progression free survival (PFS), time to-progression (TTP), disease control rate (DCR), best overall response (BOR), duration of response (DOR), duration of clinical benefit (DCB), and time to objective response (TTOR) of patients with metastatic or locally advanced microsatellite stable (MSS) colorectal cancer that have a positive and negative CPM score treated with nivolumab and relatlimab.
- 1.3.2. To assess immune objective response rate (iORR) by immune-related RECIST criteria (iRECIST).
- 1.3.3. To evaluate CPM score and determine the cut-off threshold as a predictive marker for I-O treatment in patients with MSS CRC.
- 1.3.4. To collect pre- and on-treatment biopsies to explore the association of features of the tumor microenvironment with response to therapy, including assessment of T cell subset markers (CD4, CD8, FoxP3, Granzyme A/B, CD69), immune regulation (PD-L1, PD-L2, CTLA4, LAG-3, IDO1, TIM-3), and immune cell population markers (NK, DC, B cell, MDSC).
- 1.3.5. To evaluate molecular determinants such as KRAS and BRAF status
- 1.3.6. To evaluate molecular determinants of response using next generation sequencing and other sequencing techniques.
 - Characterize the tumor mutational landscape through exomic sequencing for mutation analysis and MANA prediction.

- 1.3.7. To assess tumor burden dynamics using standard protein biomarkers when available as well as circulating biomarkers (i.e. ctDNA).
- 1.3.8. To collect peripheral blood lymphocytes to explore the association of lymphocyte activation markers with clinical response.
- 1.3.9. To evaluate clonal T cell populations in the tumor and in the periphery through T cell receptor sequencing, and to functionally assess mutation associated neoantigen-specific T cells.
- 1.3.10. To collect stool and oral wash (and/or buccal mucosal) samples at baseline and throughout treatment to explore the association of changes in the host microbiome and clinical outcome.
 - Microbial community analysis to correlate gut microbiome composition with response (OS, PFS and best overall response).
 - Whole metagenome functional profiling analysis via shotgun sequencing to correlate microbiome composition and microbial functions and pathways with response (OS, PFS and best overall response).

1.4. Study Design

This is an open-label, two stage, phase 2 study to evaluate the safety and clinical activity of nivolumab and relatlimab in patients with metastatic or locally advanced microsatellite stable (MSS) colorectal cancer that have a positive and negative composite PD-L1/Mucin (CPM) score. The primary endpoint is objective response rate (ORR) assessed using RECIST 1.1.

The trial will enroll two cohorts of MSS mCRC patients receiving 480mg nivolumab/160mg relatlimab: patients with MSS colorectal adenocarcinomas who have a positive CPM score (Cohort A); and patients with MSS colorectal adenocarcinomas who have a negative CPM score (Cohort B). The cutoff threshold $\geq 15\%$ of CPM will be used to determine CPM positivity. An additional cohort of MSS mCRC patients without biomarker selection will be enrolled to receive either 480mg nivolumab/960mg relatlimab or 480mg nivolumab/480mg relatlimab (Cohort C). As of Amendment 6, enrollment will begin to Cohort C. Enrollment to Cohorts A and B will resume once enrollment to Cohort C is complete.

As of Amendment 7, newly enrolled patients in Cohort C will receive 480mg nivolumab/480mg relatlimab Q4W. Patients previously treated in Cohort C at 960mg relatlimab will either be dose reduced to relatlimab 160mg, 480mg, or continue to receive relatlimab 960mg if they are past the 8 week safety window at the discretion of the Principal Investigator.

. Patients receiving

relatlimab 480mg or 960mg will have an increase in the frequency of safety monitoring per **Section** 9.

Each cohort will enroll up to 32 evaluable patients. The primary endpoint is objective response rate (ORR) per RECIST 1.1, and the three cohorts will be analyzed separately for the primary analysis of rate of ORR. For each cohort, the treatment will be considered inactive and of no interest for further evaluation if the ORR is 5% or less and considered active if the ORR is 20% or greater. This design allows for the simultaneous evaluation of the efficacy of the treatment and CPM as a predictive marker.

Simon two-stage minimax design is planned for each cohort. Initially, 18 patients per cohort will be treated in Stage 1. Patients will be considered evaluable if they receive at least one dose of study drug. If there is at least 1 response in the initial 18 patients in a cohort, then an additional 14 patients will be enrolled in Stage 2 for a total of 32 (18 + 14 = 32) patients in that cohort. If a total of 4 or more responses are observed in Stages 1 and 2 combined, we conclude the regimen is promising and warrants further study. This design has 90% power to reject the null response rate of 5% in favor of 20% response rate, with one-sided type 1 error 0.1.

We expect that the prevalence of a positive CPM score is 10-15% among MSS CRC patients. Therefore, we will need to pre-screen 220-320 MSS CRC patients in order to identify 32 marker positive MSS CRC patients. Assuming 95% of CRC patients are MSS, we will pre-screen a total of 235-340 CRC patients.

The study will consist of a pre-screening period (for Cohorts A and B), a screening period (within 28 days of the first dose), a treatment period, and a follow-up period. Subjects will receive treatment on 28 day cycles, and will come to clinic for dosing and/or assessments on Day 1 of each cycle and additional days for safety and immune monitoring follow up as per the study schedule in **Section 9.** No dose escalations or reductions of nivolumab or relatlimab are allowed. Complete information on study drug administration, schedule, and dosing can be found in **Section 4.1.**

The study will include a safety run-in for the first six patients for Cohorts A and B only. If more than 1 of the first 6 patients experiences an unacceptable toxicity within the first cycle, then enrollment will be halted and the overall risk-benefit ratio of the study will be reconsidered. At any time thereafter, if more than 33% of patients are observed to experience unacceptable toxicity within the first cycle, enrollment will be halted and the safety of the combination will be reevaluated. Complete unacceptable toxicity criteria can be found in **Section 4.7**.

Treatment may continue per investigator discretion, or until discontinuation due to toxicity, lack of clinical benefit as determined by the investigator, subject withdrawal, or termination of the study by the IND sponsor. Subjects may continue on treatment with radiographic disease progression if subject is clinically stable and investigator believes the treatment is providing benefit. Criteria for removal from treatment are found in **Section 4.10**.

Tumor biopsies, PBMC, serum and plasma collection, microbiome samples, and computed tomography (CT) scans or magnetic resonance imaging (MRI), if CT is contraindicated, will be obtained at baseline and during treatment for clinical assessments and correlative analyses. Tumor assessments will be made using RECIST 1.1 and iRECIST.

Subjects will return to the study site 30 (+/- 7) days after the final administration of study treatment for an end of treatment (EOT) evaluation. Subjects will be considered in the treatment period until 30 days after the last dose of study drug. After completion of treatment and EOT assessments, all subjects will continue to be followed per **Section 4.12**.

Information on progression-free survival and overall survival may continue to be gathered for supplementary analyses after the completion of the primary analysis.

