4. TREATMENT PLAN

4.1. Agent Administration

Treatment will be administered on an outpatient basis. Appropriate dosing delays are described in **Section 5.** No investigational or commercial agents or therapies other than those described below in **Table 2** may be administered with the intent to treat the patient's malignancy.

Table 2: Regimen Description

REGIMEN DESCRIPTION									
Agent	Premedications; Precautions	Administration Type	Dose	Route	Schedule	Cycle Length			
Cohort A/B: Nivolumab/ Relatlimab	No prophylactic pre-medication will be given unless indicated by previous experience in an individual subject per	Co-administration	480mg/160mg	IV infusion over 60 (+/-15) min*					
Cohort C: Nivolumab/ Relatlimab		Sequential**	480mg/960mg or 480mg/480mg ***	Each drug infused IV over 30 (+/-10) min*	Day 1	28 days			
	Section 4.2	Co-administration	480mg/160mg ***						

^{*}Infusion times are approximate and may be adjusted based on subject tolerability.

^{**} Order of administration is nivolumab followed by relatlimab. Subjects should be observed for a minimum of 30 minutes between each infusion.

***Patients enrolling during or after Amendment 7 will receive nivolumab/relatlimab 480mg/480mg. Patients who enrolled prior to Amendment 7 and are within 8 weeks of their first dose will be dose reduced to nivolumab/relatlimab 480mg/160mg or 480mg/480mg at the discretion of the Principal Investigator. Patients who are past 8 weeks from their first dose may continue to receive nivolumab/relatlimab 480mg/960mg or be dose reduced to nivolumab/relatlimab 480mg/160mg or 480mg/480mg at the discretion of the Principal Investigator.

Please see Section 5.2 for guidance regarding dosing delays.

Antiemetic medications should not be routinely administered prior to dosing of drugs. See **Section 4.2.1** for subsequent premedication recommendations following an infusion reaction.

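### Cohort C mixes 960 mg and 480 mg relatlimab starters, but the planned adverse event and response summaries are per cohort only, so neither is shown by dose

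*Combined protocol and SAP*

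**What the plan says.** **Treatment.** Section 1.4 defines Cohort C as patients who "will be enrolled to receive either 480mg nivolumab/960mg relatlimab or 480mg nivolumab/480mg relatlimab (Cohort C"), and from Amendment 7 "newly enrolled patients in Cohort C will receive 480mg nivolumab/480mg relatlimab Q4W". Under the footnote to Table 2 in Section 4.1, earlier enrollees "within 8 weeks of their first dose will be dose reduced to nivolumab/relatlimab 480mg/160mg or 480mg/480mg", at the Principal Investigator's discretion. It adds: "Patients who are past 8 weeks from their first dose may continue to receive nivolumab/relatlimab 480mg/960mg or be dose reduced", the lower options again being 480 or 160 mg. One cohort therefore holds two starting doses and up to three received doses.

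**Objectives.** Section 1.1 asks for the ORR in patients "without prospective biomarker selection treated with nivolumab and relatlimab", with no dose named. The only secondary objective, in Section 1.2, is "To assess safety and characterize toxicities of nivolumab in combination with relatlimab".

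**Analysis.** Section 12.1 analyzes the three cohorts separately, with one ORR and 95% CI each. Every cohort uses the same Simon rule: 18 patients, then 14 more after at least 1 response. With 4 or more responses in 32, "we conclude the regimen is promising and warrants further study". Section 12.2 lists AEs individually, summarizes their incidence by cohort, and tabulates toxicity by type and grade. The safety measures in Section 10.2 carry no dose dimension. Nothing in Sections 10 or 12 plans a summary by relatlimab dose.

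**The concern.** The protocol separates the doses on safety grounds everywhere except in the planned outputs. New patients start lower, and 960 mg patients inside the 8-week window must be reduced. Patients on 480 or 960 mg have extra weekly AE visits, troponin and CPK through Cycle 3 Day 1 (Section 9.2, footnotes 3 and 9). The planned AE table then merges the two starting doses.

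This matters most for the toxicity objective. Section 1.4 states: "The study will include a safety run-in for the first six patients for Cohorts A and B only". Those cohorts receive 160 mg, so the run-in says nothing about 480 or 960 mg. Cohort C is where this trial would learn about toxicity at the higher doses, and the planned table gives one figure for both.

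The same applies to response, with less force. A single Cohort C ORR does not show whether the responses came from patients who started at 480 mg, the dose that new Cohort C patients now receive.

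**Working it through.** **1. The plan's own figures.** Inputs from Section 12.1: null ORR 5%, target 20%, n1 = 18, continue with at least 1 response, n2 = 14, success with at least 4 of 32.

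P(success | p) = sum over x = 1 to 18 of Bin(x; 18, p) × P(Bin(14, p) ≥ 4 − x)

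- p = 0.05: 0.072, within the stated one-sided 0.1.
- p = 0.20: 0.901, matching the stated 90%.

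The rule reproduces, and nothing below alters it.

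**2. What a pooled AE rate shows.** Let k be the number of 960 mg starters among 32. The documents do not give k or any AE rate by dose, so both are assumed. Take a toxicity with rate 10% in 480 mg starters and 30% in 960 mg starters.

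Expected pooled rate = [(32 − k) × 0.10 + k × 0.30] / 32

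| k | Sum | Pooled rate |
|---|---|---|
| 1 | (3.1 + 0.3)/32 | 10.6% |
| 3 | (2.9 + 0.9)/32 | 11.9% |
| 6 | (2.6 + 1.8)/32 | 13.8% |
| 12 | (2.0 + 3.6)/32 | 17.5% |

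For k up to 6 the pooled rate stays within 4 points of the 480 mg rate, and the 30% at 960 mg disappears. At k = 12 the pooled rate describes neither dose.

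**3. What a pooled ORR shows.** Suppose k = 6 and 4 of 32 respond (12.5%, exact 95% CI 3.5–29.0%). That total is compatible with, for example:

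- 4/26 in 480 mg starters (15.4%, CI 4.4–34.9%) and 0/6 in 960 mg starters (upper limit 45.9%);
- 2/26 (7.7%, CI 0.9–25.1%) and 2/6 (33.3%, CI 4.3–77.7%).

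The planned output is the same in both cases. The intervals are too wide to establish a difference, so the split can only be descriptive.

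**4. Precision lost by splitting.** With zero events the exact two-sided 95% upper limit is 1 − 0.025^(1/n).

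- Pooled, 0/32: 10.9%.
- 480 mg starters at k = 6, 0/26: 13.2%.
- 960 mg starters at k = 6, 0/6: 45.9%.

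The 480 mg column loses little; the 960 mg column is imprecise whatever is done.

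**5. Why starting dose alone is not enough.** Section 9.2, footnote 15, puts the first on-study scan at week 12 ± 2, so at week 10 at the earliest. A 960 mg starter reduced within 8 weeks would normally have any response documented on a lower dose. AEs raise the same question of which dose was current at onset.

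**The case against.** The strongest reply is that the plan contains no error. The Cohort C objective names no dose, Section 12.1 openly defines the cohort as 960 mg or 480 mg, and Section 12 is a short analysis section that does not forbid a by-dose display. AEs are listed individually, starting dose follows from enrolment before or after Amendment 7, and the serious adverse event (SAE) form in Appendix E has a dose field. All of this stands, and it makes the point an improvement rather than a defect. But a listing is not a summary, and the form covers SAEs only.

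A second reply is that the 960 mg column would mix 960, 480 and 160 mg exposure in what may be very few patients, at a starting dose no longer given to new patients. That also stands, and it is why dose at onset and at response should be flagged.

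A third is that by-dose tables at the end of the study do not make up for a missing Cohort C run-in. Correct: the run-in bears on real-time monitoring, which is covered by the extra weekly visits, weekly safety meetings (Section 11.2) and Safety Monitoring Committee oversight (Section 11.3). It is cited here only because it means that Cohort C is the source of higher-dose toxicity data.

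A reader might go further and infer that pooling inflates the type I error of Cohort C, or that its stated error rates mislead about 480 mg. The documents do not support this. Those rates are stated for each cohort, and no passage assigns them to 480 mg. If the ORR is 5% at 480 mg but higher at 960 mg, the pooled ORR exceeds 5%. With k = 6 and 20% at 960 mg, for example, it is (6 × 0.20 + 26 × 0.05)/32 = 7.8%. A positive conclusion is then not a false rejection of the cohort's null. No disclaimer is needed for a claim the plan does not make.

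**Conclusion.** Cheap improvement. The planned Cohort C tables merge two starting doses that the protocol separates for safety, and so serve the toxicity objective less well than a by-dose table would. The case is stronger for AEs than for ORR.

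That no by-dose summary is planned rests on the text: Sections 12.1 and 12.2 show no sign of redaction here, though text beside the dose-change rules in Sections 1.4 and 5.1 is missing. The size rests on assumptions. The number of 960 mg starters, the AE rates and any response difference are not in the documents; if few patients started at 960 mg or the doses behave alike, the gain is small. The pooled 18+14 rule, the 90% power and the 0.1 type I error are valid as stated.

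**What to change.** 1. In Section 12.2, tabulate Cohort C AEs by starting relatlimab dose (480 mg and 960 mg) beside the cohort total, flagging dose at AE onset.
2. In Section 12.1, add a descriptive Cohort C ORR with exact 95% CI by starting dose, flagging later dose changes and dose at response.
3. Leave the pooled 18+14 rule and its stated error rates unchanged.

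This takes one or two sentences and extra table columns, with no added patients and no change to the decision rule. Starting dose is already recoverable. Dose at onset or at response should come from the dosing records, assuming the dose of each infusion is recorded: no passage says that the AE listing carries it, and the SAE form labels 160 mg as Cohort A/B only, with no labelled option for a Cohort C patient reduced to 160 mg.

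The price is wide intervals in the smaller group (1/6 gives 16.7%, exact 95% CI 0.4–64.1%) and a 960 mg-start column with mixed exposure. A footnote to each table should say both.

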12. STATISTICAL CONSIDERATIONS

12.1. Study Design/Endpoints

Sample Size

This is an open-label, two stage, phase 2 study to evaluate the safety and clinical activity of nivolumab and relatlimab in patients with metastatic or locally advanced microsatellite stable (MSS) colorectal cancer that have a positive and negative composite PD-L1/Mucin (CPM). The primary endpoint is objective response rate (ORR) assessed using RECIST 1.1.

The trial will enroll two cohorts of MSS mCRC patients receiving 480mg nivolumab/160mg relatlimab: patients with MSS colorectal adenocarcinomas who have a positive CPM score (Cohort A); and patients with MSS colorectal adenocarcinomas who have a negative CPM score (Cohort B). The cut-off threshold $\geq 15\%$ of CPM will be used to determine CPM positivity. An additional cohort of MSS mCRC patients without biomarker selection will be enrolled to receive 480mg nivolumab/960mg relatlimab or 480mg nivolumab/480mg relatlimab (Cohort C).

Each cohort will enroll up to 32 evaluable patients. The primary endpoint is objective response rate (ORR) per RECIST 1.1, and the three cohorts will be analyzed separately for the primary analysis of rate of ORR. For each cohort, the treatment will be considered inactive and of no interest for further evaluation if the ORR is 5% or less and considered active if the ORR is 20% or

greater. This design allows for evaluating the efficacy of the treatment and CPM as a predictive marker simultaneously.

Simon two-stage minimax design is planned for each cohort. Initially, 18 patients per cohort will be treated in stage 1. Patients will be considered evaluable if they receive at least one dose of study treatment. If there is at least 1 response in that cohort then an additional 14 patients will be enrolled in stage 2 for a total of 32 patients in that cohort. If a total of 4 or more responses are observed in stage 1 and 2 combined, we conclude the regimen is promising and warrant further study. This design has 90% power to reject the null response rate of 5% in favor of 20% response rate, with one-sided type 1 error 0.1.

We expect that the prevalence of a positive CPM score is 10-15% among MSS CRC patients. Therefore, we will need to screen 220-320 MSS CRC patients in order to identify 32 marker positive MSS CRC patients. Assuming 95% of CRC patients are MSS, we will screen a total of 235-340 CRC patients.

Statistical Analyses

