The primary endpoint is objective response rate, defined as complete response (CR) or partial response (PR) per RECIST 1.1. Objective response rate (ORR) will be estimated as the proportion of subjects whose best overall response is either a CR or PR with corresponding 95% CI. The primary population for the analysis is all subjects who receive at least one dose of study drug, and have at least one post-baseline tumor assessments or discontinue due to toxicity or clinical progression prior to post-baseline tumor assessments.

Exploratory endpoints include progression-free survival (PFS), overall survival (OS), and duration of response (DOR). PFS is defined as the time from the first day of study treatment to the date of the first documented tumor progression or death due to any cause, whichever occurs first. Subjects who did not progress or die will be censored on the date of their last tumor assessment. Kaplan-Meier curves will be used to summarize PFS. Overall survival (OS) is the time from the first day of study treatment to the date of death due to any cause. A subject who has not died will be censored at last known date alive. Kaplan-Meier curves will be used to summarize OS. Among patients with an objective response, DOR is defined as the time between the date of initial complete or partial response to the date of the first documented tumor progression or death due to any cause. Subjects who neither progress nor die will be censored on the date of their last tumor assessment. Summary statistics will be presented for DOR.

For biomarkers, potential relationships between biomarker data and efficacy or safety endpoints will be investigated aimed at identifying baseline biomarkers that may be used to prospectively identify subjects likely (or not likely) to respond to the treatment and to identify subjects who may be predisposed to having adverse reactions to treatment. These exploratory biomarker analyses will be completed with biomarkers measured in blood and in tumor samples.

The performance of the PD-L1/mucin composite score (CPM) in predicting treatment response will be further evaluated. ROC analysis based on logistic regression will be used to assess the

prediction accuracy, and the cutoff threshold for identifying patients who may benefit the therapy will be validated.

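### The plan says its design evaluates CPM as a predictive marker, but it prespecifies no CPM-positive versus CPM-negative response difference and treats every patient, so it can show association with response only

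*Combined protocol and SAP*

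**What the plan says.** Section 1.4 sets up Cohort A (CPM at or above 15%) and Cohort B (CPM below 15%) on one regimen, with relatlimab 160 mg. Cohort C is not selected by CPM and receives relatlimab 480 or 960 mg, with some earlier patients reduced to lower doses. Each cohort has its own Simon two-stage test, described by "This design has 90% power to reject the null response rate of 5% in favor of 20% response rate, with one-sided type 1 error 0.1". Section 12.1 adds that "the three cohorts will be analyzed separately for the primary analysis of rate of ORR".

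Directly after the per-cohort activity criteria, Section 1.4 says "This design allows for the simultaneous evaluation of the efficacy of the treatment and CPM as a predictive marker". Section 12.1 says the same in the same position: "This design allows for evaluating the efficacy of the treatment and CPM as a predictive marker simultaneously".

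Two further places bear on this. Objective 1.3.3, on CPM and its cutoff, is listed as exploratory. Under Statistical Analyses, Section 12.1 says "The performance of the PD-L1/mucin composite score (CPM) in predicting treatment response will be further evaluated", using ROC analysis from logistic regression, and adds that the cutoff will be validated. Section 8.1 says Cohort C will have CPM scored on archived tissue after enrolment.

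**The concern.** The claim describes a property that the per-cohort tests lack. A verdict of promising in A and not promising in B is two separate comparisons with 5%. It does not estimate how far response differs by CPM. Section 12.1 gives no A-versus-B difference, interval, test, power, or rule for reading the two results together.

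There is also no untreated or differently treated group. A marker is predictive if it identifies patients whose benefit from the treatment, relative to not having it, differs. With everyone on the combination, a higher response rate, longer PFS or longer OS in CPM-positive patients could be prognostic. This matters most for PFS and OS, which objective 1.3.1 assesses by CPM status.

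The marker question is why A is split from B, and why 220–320 MSS patients are to be pre-screened. A reader who takes the quoted sentence at face value may contrast the two verdicts and report a marker effect that chance alone could produce.

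**Working it through.** **Inputs (Sections 1.4 and 12.1).** Null ORR 5%; target 20%; one-sided error limit 0.10; 18 patients in stage 1; continue with at least 1 response; 14 more in stage 2; promising with at least 4 responses in 32. The documents give no expected ORR by CPM status, so the common true ORR is varied as an assumption. A and B are taken as independent.

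**Step 1: reproduce the plan's design.** The probability that a cohort passes at true ORR p is

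G(p) = Σ (x from 1 to 18) P(X₁ = x) · P(X₂ ≥ max(0, 4 − x)), with X₁ ~ Bin(18, p) and X₂ ~ Bin(14, p).

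- p = 5%: 0.3763×0.0301 + 0.1683×0.1530 + 0.0473×0.5123 + 0.0109 = 0.072
- p = 20%: 0.0811×0.5519 + 0.1723×0.8021 + 0.2297×0.9560 + 0.4990 = 0.9015

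The last term in each line is the chance of 4 or more responses already in stage 1. Power agrees with the stated 90%. An exact error of 0.072 under a limit of 0.10 is normal for a discrete design. A search for the minimax design returns the same 18/32 plan, so the per-cohort tests are sound.

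**Step 2: contrast the verdicts when CPM has no effect.** If A and B share one true ORR, P(A passes, B fails) = G(1 − G). This peaks at G = 0.5, so it cannot exceed 25%.

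| Common true ORR | G | A passes, B fails | Cohorts disagree, either direction |
|---|---|---|---|
| 2% | 0.004 | 0.4% | 0.7% |
| 5% | 0.072 | 6.7% | 13.4% |
| 10% | 0.393 | 23.9% | 47.7% |
| 12% | 0.538 | 24.9% | 49.7% |
| 15% | 0.720 | 20.2% | 40.3% |
| 20% | 0.9015 | 8.9% | 17.8% |
| 30% | 0.994 | 0.7% | 1.3% |

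The opposite error also occurs. With true ORRs of 20% and 10%, both cohorts pass with probability 0.9015 × 0.393 = 35%, which hides a real difference.

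**Step 3: what a split verdict can look like.** A result of 4/32 against 3/32 is promising against not promising. The difference is 12.5% − 9.4% = 3.1 points. Wilson limits are 5.0–28.1% and 3.2–24.2%, and the Newcombe interval is

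- lower: 3.1 − √(7.5² + 14.8²) = −13.5 points
- upper: 3.1 + √(15.6² + 6.1²) = +19.9 points

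Fisher's exact two-sided p is 1.00.

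**Step 4: what a direct comparison could deliver.** Exact power of Fisher's test, 32 against 32, true ORRs 20% and 5%:

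- one-sided 0.10: 0.607 (0.606 if stage-1 stopping is allowed for)
- one-sided 0.025, the level that matches a 95% CI: 0.276

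At a common ORR of 10–12%, the one-sided 0.10 Fisher test favours CPM falsely in about 5% of trials, against 24–25% for contrasted verdicts.

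**The case against.** The best defence is that the plan nowhere says CPM will be judged by comparing verdicts. The rule of at least 4 responses serves only to call the regimen promising. The CPM objective is exploratory, and Section 12.1 does plan an analysis that links CPM to response across patients. A reader might infer that CPM-positive and CPM-negative patients are never related to each other. The documents do not support that, because a logistic/ROC analysis uses both groups. Section 12.1 also gives the biomarker aim as finding patients likely or unlikely to respond, which is close to an association claim.

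This stands, but it leaves the defect in place. The ROC analysis names no population and does not say whether Cohort C enters. It gives no ORR difference at the 15% cutoff on which the cohorts are built, and it too uses treated patients only. Exploratory status excuses low power; it does not excuse crediting the design with a property it lacks.

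A reader might also infer that a false predictive conclusion is likely. The figures do not support that. A false split in CPM's favour never exceeds 25%, and it is 6.7% and 8.9% at the plan's own reference rates of 5% and 20%. The disagreement rates near 50% count both directions, and half of those splits go against CPM. The background sections report almost no responses to earlier PD-1 or PD-L1 monotherapy in this disease; if the true ORR were as low as 2%, the false split would be 0.4%.

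**Conclusion.** The point holds as a matter of what the trial may claim, and it should be fixed. The wording in Sections 1.4 and 12.1 goes beyond the design: no A-versus-B ORR difference is prespecified, and without a comparator the data can support association of CPM with response to the combination, not prediction of treatment benefit.

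Contrasted verdicts would favour CPM by chance in 6.7% to about 25% of trials for common true ORRs between 5% and 20%, with the peak near 11%. These figures assume independent cohorts, the stated stopping rule, and 32 evaluable patients wherever stage 2 opens. They describe an inference that the quoted sentence invites, not one the plan prescribes. The per-cohort primary tests are unaffected.

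**What to change.** In Section 12.1:

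- Prespecify the A-minus-B difference in ORR with a 95% CI (Newcombe or exact), in the same-dose Cohorts A and B, as the CPM-by-response estimate alongside the ROC analysis.
- Restrict the main ROC analysis to Cohorts A and B, with Cohort C added as a sensitivity analysis because its relatlimab doses differ.
- State that discordant go/no-go results are not evidence for CPM.
- If power is stated, give it with its level: Fisher's exact test at 32 against 32, 20% against 5%, has about 61% at one-sided 0.10 and about 28% at one-sided 0.025. The 61% figure should not stand beside a 95% CI without its level.

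In Sections 1.4 and 12.1, replace *predictive marker* with *association of CPM with response to the combination*.

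The cost is one extra table and a more modest marker claim. No new arm, patients or assessments are needed.
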